Participants randomized to the facilitated DOT arm will attend the Mulago ISS clinic on a weekly basis to ingest 3HP medication under direct observation. DOT will be defined as a designated clinic staff member observing ingestion of each dose of 3HP. Additionally, participants randomized to facilitated DOT will receive:

1. DOT cards with instructions to present directly to the pharmacy for a pharmacy-only visit, without the need to wait in the general queue.
2. Automated SMS or interactive voice response (IVR) phone call reminders at no cost to participants the day before each appointment.
3. A fixed level of reimbursement (~\$5-8/visit) for each weekly visit, conditional on either directly observed therapy or evidence of an adverse event that would preclude further treatment.

Participants who fail to return for a scheduled appointment within 24 hours will receive an SMS or IVR phone call reminder for three consecutive days after the missed appointment.

Arm 2: Facilitated SAT

Participants randomized to the facilitated SAT arm will take their first dose of medication under direct observation and be provided with a 4-week supply of 3HP to take weekly via self-administration. Participants will be asked to return to the Mulago ISS clinic after completing their 5th dose to review adherence data with the Mulago ISS clinic pharmacy technician and receive 5 additional doses of 3HP (doses 7-11). At the scheduled refill visit (dose 6) and the end-of-treatment visit (dose 12), participants will ingest 3HP doses under direct observation. Additionally, participants will receive:

1. 99DOTS-based digital adherence technology to monitor and promote adherence.
2. Weekly check-ins via two-way SMS or IVR phone call for dosing reminders and messaging asking "Are you well?" (or other similar message, as determined in our formative research phase), to serve as an alternative to weekly visits with a health worker to inquire about potential side effects
3. A fixed level of reimbursement (~\$5-8/visit) for the refill and end-of-treatment visit, conditional on either directly observed therapy or evidence of an adverse event that would preclude further treatment.

Participants who fail to return for a scheduled appointment within 24 hours will receive an SMS or IVR phone call reminder for three consecutive days after the missed appointment.

Arm 3: Patient Choice between facilitated DOT and facilitated SAT

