Participants randomized to the Patient Choice between facilitated DOT and facilitated SAT arm will be offered a choice between arms 1 and 2. A research nurse will review each section of the decision aid with participants, discuss values and preferences, and, after addressing any questions, ask participants to select facilitated DOT or facilitated SAT. Participants will have the option to switch between DOT and SAT at any time. The reason for switching and time spent under each strategy will be recorded.

Eligibility Criteria

To be included in the randomized trial, patients will have to meet all of the following inclusion criteria and none of the exclusion criteria:

1. Inclusion Criteria:

- a. HIV-positive client engaged in care at the Mulago ISS clinic
- b. Weight $\geq 40\text{kg}$
- c. Age 18 years or older
- d. Capacity to provide informed consent in English or Luganda

(From our experience conducting similar studies at the Mulago ISS clinic, the majority of patients receiving care at the clinic are able to communicate using the Luganda language. For example, while

conducting patient Knowledge, Attitudes and Practices (KAP) interviews during the formative phase, 21/25 (84%) participants opted for Luganda and only four of the 25 opted for English as the language for the interview. Therefore, in addition to Luganda, we selected English as the other preferred language for the study)

2. **Exclusion Criteria:**

- a. Suspicion of active TB based on positive WHO symptom screen AND elevated POC CRP, or current or planned TB treatment
- b. Actively taking an antiretroviral medication contraindicated for use with rifapentine under contemporary WHO or Ugandan policy
- c. Contact of a TB patient with known resistance to isoniazid or rifamycins
- d. Women who are pregnant, breast feeding or intending to get pregnant in the next 120 days. Note: women who become pregnant while on 3HP will be recommended to continue and complete 3HP treatment per Uganda 2020 Uganda National Guidelines, and will be monitored for side effects as per the study protocol ²⁶
- e. Prisoners
- f. Previously completed treatment for active TB or at least 6 months of isoniazid preventive therapy within past 2 years
- g. Not intending to remain within 25 km of the Mulago ISS clinic during the study period or to receive further care at the Mulago ISS clinic
- h. Lack of access to a mobile telephone or lack of willingness to receive SMS reminders/IVR phone calls

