^a 3HP treatment may last up to 16 weeks^b Patients randomized to choice arm only^c Time-and-motion studies will be performed on 40 randomly selected days (one day per week throughout the year, stratified by day of week). We anticipate that this will capture up to 250 unique participant visits per arm (750 total).^d Patient costing surveys will include 50 participants from each arm, or 150 participants total^e Only if symptomatic, except at end of follow-up.^f 24 participants/arm

Outcome Measures

Primary Outcome (Effectiveness of delivery options)

Outcome	Numerator	Denominator
Proportion accepting and completing 3HP treatment	Number who take at least 11 of 12 doses within 16 weeks of treatment initiation	Number randomized

Secondary Outcomes (Quantitative)

Outcome	Numerator	Denominator
REACH		
Treatment acceptance	Number taking at least one dose of 3HP	Number randomized
EFFECTIVENESS		
Treatment completion	Number who take at least 11 of 12 doses within 16 weeks of treatment initiation	Number taking at least one dose of 3HP

Cost-effectiveness (overall)	(Cost in Arm A – cost in Arm B) from societal perspective	(DALYs averted in Arm A – DALYs averted in Arm B) from societal perspective
Cost-effectiveness (health system)	As above, but from health system/provider perspective	As above, but from health system/provider perspective
Cost-effectiveness (patient)	As above, but from patient perspective	As above, but from patient perspective
Safety	Number for whom treatment discontinued due to adverse events or intolerance.	Number taking at least one dose of 3HP
Cumulative incidence of TB at 16 months	Number diagnosed with TB during 16-month follow-up	Risk set*
Cumulative incidence of TB at 28 months	Number diagnosed with TB during 28-month follow-up	Risk set*
ADOPTION		
All Participants		
Visit Cost Reimbursement	Number of visits for which reimbursement provided on same day	Total number of DOT/refill visits
Time to complete clinic visit	Mean and median number of minutes for each DOT/refill visit	--
SMS or IVR phone call reminders delivered	Number of SMS or IVR phone call dosing or clinic visit reminders delivered	Total number of SMS reminders scheduled to be sent
SMS or IVR phone call reminders following missed appointments	Number of SMS or IVR phone call dosing or clinic missed appointment reminders delivered	Number of participant weeks with 3HP missed appointments
Screening for active TB	Number screened for active TB during DOT visits	Total number of DOT visits

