- Assessing our primary outcome using multivariable log-binomial models that adjust for the characteristics measured in the baseline survey (e.g., ART status). If multivariable log-binomial models fail to converge, we will use a modified Poisson regression with robust estimates of variance.³⁴ Comparison will be made to logistic regression models as well.
- Assessing our primary outcome to estimate a per protocol estimand that reflects the difference in treatment completion rates in patients that actually start treatment. Causal inference methods such as inverse probability weighting will be used to minimize bias in this estimator, full details will be given in the statistical analysis plan.

- Assessing our primary outcome to estimate a per protocol estimand for the comparison of DOT vs SAT irrespective of treatment arm in treatment competition rates (combining participants that choose to start on SAT with participants in the SAT arm and combining participants that choose to start on DOT with participants in the DOT arm). This analysis will be repeated as an 'as treated' analysis classification participants based on which delivery strategy they actually received for the majority of doses irrespective of which arm they were allocated to or which delivery method they started on in the choice arm. Causal inference methods such as inverse probability weighting will be used to minimize bias in this estimator, full details will be given in the statistical analysis plan.

Qualitative data analysis plan

All interviews will be audio recorded. The recordings will be transcribed with no names or identifying information. The transcribed texts will be cleaned (quality reviewed against the original audio). The final transcripts will be stored in word-processed files on a password-protected computer. The files will be securely uploaded into Dedoose software where open coding will be applied to generate codes and themes. Thematic groupings will be developed and reviewed to identify emergent themes within each domain of the coding framework and quotes that best represent each domain. Thematic interpretation will include collaborative development of a coding framework and detailed coding of transcripts. Trained research team members experienced in qualitative data analyses will undertake data analyses.

V. Data Management

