### 3.2 Dataset assembly, cleaning and creation of new variables

Datasets will be extracted from REDCap, transferred to Stata statistical software, and re-arranged into working analytic files. At first, long format shall be used, but after cleaning and generation of relevant variables, data will be reshaped into a wide format for final analyses. Working analytic datasets will be checked, each variable at a time, for completeness, logical range, and consistency accuracy. Patient adherence data, for both directly observed and digitally confirmed doses, are stored in Everwell 99DOTS adherence database. Dosing reports extracted from the Everwell database containing detailed information on patient adherence, including date and time stamps associated with each dose taken, will be merged with trial data in order to summarize patient treatment adherence and overall treatment completion statistics.

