effectiveness of each delivery option, with a target of >80%, and 3) comparisons of risk ratios and 97.5% two-sided CIs of effectiveness between arms, adjusted for unbalanced characteristics or pre-specified characteristics measured in the baseline survey. We will assess for differences in the ITT and PP analysis populations by comparing baseline characteristics such as age, sex, antiretroviral therapy (**ART**) status, time on ART and prior TB.

3. **Assessing our primary outcome to estimate an as treated estimate that reflects the difference in treatment completion rates in patients** classifying participants based on which delivery strategy they actually received, irrespective of which arm they were allocated to. This will involve 1) allocating choice participants to either DOT or SAT arm, 2) making unadjusted comparisons of risk ratios and 97.5% two-sided CIs of effectiveness between arms, 3) simple calculation (using the exact binomial CIs) of the effectiveness of each delivery option, with a target of 80% and 4) comparisons of risk ratios and 97.5% two-sided CIs of effectiveness between arms, adjusted for unbalanced characteristics or pre-specified characteristics measured in the baseline survey.

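### In the as-treated DOT-versus-SAT analysis, the majority-of-doses rule lets a choice-arm switcher's outcome help decide her group, and the SAP gives no other rule

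*Protocol*

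**What the plan says.** The third bullet of the secondary analyses (Protocol, Statistical Considerations) plans a pooled comparison of DOT with SAT in two versions. The first groups by starting strategy, for example "combining participants that choose to start on SAT with participants in the SAT arm". The second, called as treated, groups people "based on which delivery strategy they actually received for the majority of doses irrespective of which arm they were allocated to". The bullet does not say whether the majority is of doses taken or doses scheduled, or how ties and people with no doses are handled. It adds that "Causal inference methods such as inverse probability weighting will be used to minimize bias in this estimator" and leaves the details to the SAP.

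The outcome compared is the primary one, whose numerator in the Protocol's Outcome Measures is "Number who take at least 11 of 12 doses within 16 weeks of treatment initiation". Switching is described for the choice arm only: "Participants will have the option to switch between DOT and SAT at any time" (Study Arms, Arm 3).

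SAP 3.5 item 3 lists an as-treated sensitivity analysis, "classifying participants based on which delivery strategy they actually received, irrespective of which arm they were allocated to". Choice participants are to be placed in DOT or SAT, with unadjusted comparisons and comparisons adjusted for baseline characteristics. It contains no majority wording, rule for switchers, weighting or grouping by starting strategy. SAP 2.3 says that the SAP prevails over the Protocol.

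**The concern.** An as-treated group should not be defined by something that the outcome determines. Here the group is settled after treatment starts, by counting doses, and the outcome is a count of the same doses.

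Take a participant who switches from DOT to SAT after dose 5. If she completes, she has 6 or 7 SAT doses and is classed as SAT. If she fails with 10 doses or fewer, she has at most 5 SAT doses, so she is classed as DOT or is a tie. Among such switchers the new strategy collects every success and no failure, whatever the two strategies really achieve.

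DOT versus SAT is a practical question for clinics, and the Protocol's Background says that weekly clinic visits may cost patients a great deal of time and money. Switching mainly from DOT to SAT is therefore plausible, and that is the pattern that produces a false advantage for SAT. The SAP's silence does not prevent this: the Protocol's majority rule is the only written rule that an analyst could apply.

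**Working it through.** **Plan's figures.** The documents give no figure for this analysis; only the arm size is borrowed from them. That size reproduces closely. For 70% versus 80%, two-sided alpha 0.025, power 0.90 and a continuity correction, the requirement is 483 per arm, and 483/0.9 = 537 after the Protocol's 10% loss, against 552 stated.

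**Inputs.** From the documents: 552 per arm, switching in the choice arm only, success = at least 11 doses. Assumed: the choice arm splits 276/276, so 552 + 276 = 828 start each strategy; everyone starts; true completion is 75% on both; failures are spread evenly over 1 to 10 doses; ties stay with the starting strategy; a fraction s of the 276 choice-arm DOT starters would switch to SAT after dose k if still on treatment; switching is unrelated to prognosis.

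**Step 1: who moves.** With d doses in all, a switcher has k old and d - k new doses and moves only if d > 2k. For k = 1 to 5 every completer moves (k = 5: 11 - 5 = 6 > 5). For k = 6 or more nobody moves (12 - 6 = 6 is a tie). Among failures who reached the switch, the share left in the old strategy is 1/9, 2/8, 3/7, 4/6 and 5/5 for k = 1 to 5. Sorting is slight for very early switches and complete at dose 5.

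**Step 2: formula.** Let C completers and F failures move. 828 x 0.75 = 621, so

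DOT = (621 - C)/(828 - C - F), SAT = (621 + C)/(828 + C + F).

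**Step 3: worked cases at s = 20%** (276 x 0.20 = 55.2 people: 41.4 completers, 13.8 failures).

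- All after dose 5: C = 41.4, F = 0. DOT = 579.6/786.6 = 73.7%; SAT = 662.4/869.4 = 76.2%; gap 2.5 points.
- Spread over doses 1-5: the shares of all failures that move are 0.8, 0.6, 0.4, 0.2 and 0, mean 0.4, so F = 5.52. DOT = 579.6/781.08 = 74.2%; SAT = 662.4/874.92 = 75.7%; gap 1.5 points.
- Spread over doses 1-10: half the switches move nobody, so C = 20.7 and F = 2.76. DOT = 600.3/804.54 = 74.6%; SAT = 641.7/851.46 = 75.4%; gap 0.75 points.

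**Step 4: range.** False SAT advantage in percentage points:

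| Switching (DOT to SAT) | Doses 1-10 | Doses 1-5 | All after dose 5 |
|---|---|---|---|
| 0% | 0 | 0 | 0 |
| 10% | 0.4 | 0.75 | 1.3 |
| 20% | 0.75 | 1.5 | 2.5 |
| 30% | 1.1 | 2.3 | 3.8 |
| Equal in both directions | 0 | 0 | 0 |

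**Step 5: other assumptions.** With 80% completion and a constant dropout hazard per dose, 20% one-way switching gives 0.7, 1.3 and 2.1 points in the same three columns. In the last case the chance of a false finding at alpha 0.025 is 12.4%. Grouping by starting strategy gives 0.0 points in every scenario.

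**The case against.** The strongest reply is that the governing text no longer contains the rule. The SAP prevails and says only that people are classed by what they received. That is correct, and it narrows the point: what remains is that nothing replaces the majority rule for switchers, and the promised weighting details are absent. The Protocol does not confine its weighting to baseline factors, so the criticism falls on the SAP's omission and not on weighting as such.

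The second reply is that the effect is small and conditional. This also stands. It needs switching that is mostly one way and by dose 5, and the documents give no rate.

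Third, if the majority is counted over the 12 scheduled doses, the group no longer depends on doses taken after the switch. For switches at doses 1-5 about half the gap then remains (0.75 points at 20%, 1.1 at 30%), because a person must stay on treatment long enough to switch. The Protocol does not choose between the two readings, and neither is free of bias.

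A reader might infer something larger: that the rule sorts completers from failures across the whole trial. The argument would be that SAT participants "take their first dose of medication under direct observation", so one who stops after dose 1 has all her doses observed and becomes a DOT failure. If 2.5% of 828 SAT starters (20.7) did so, SAT would be 621/807.3 = 76.9% and DOT 621/848.7 = 73.2%, a gap of about 3.75 points; at 5% it would be about 7.5. The documents do not support this reading. The rule refers to the delivery strategy, not to where a pill was swallowed. Arm 2 defines facilitated SAT as including observed doses 1, 6 and 12, and the stopping rates are assumed. SAP 3.2 says that "Patient adherence data, for both directly observed and digitally confirmed doses, are stored in Everwell 99DOTS adherence database", but that concerns storage, not classification. One clarifying sentence would close the question.

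**Conclusion.** The point holds for choice-arm switchers in this secondary analysis. Their group depends partly on the outcome, adjustment for baseline characteristics cannot correct that, and the SAP supplies no alternative rule. Participants who do not switch are classed correctly whatever their dose count, and the intent-to-treat primary analysis is untouched.

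The size rests on assumptions, since no switching rate is documented. Across the one-way scenarios with 10-30% switching the false SAT advantage runs from about 0.4 to 3.8 points. It is about 1.3 points or less at 10% switching, and zero with no switching or equal switching both ways. The 10-point minimum important difference was set for choice versus DOT and is not a direct yardstick here. The change is worth making because it is simple, but the point does not threaten the trial's main conclusion.

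**What to change.** - Remove the majority-of-doses rule from the Protocol's third secondary-analysis bullet, and do not carry it into SAP 3.5 item 3.
- In SAP 3.5 item 3, run the pooled DOT-versus-SAT comparison by starting strategy: assigned strategy in the DOT and SAT arms, strategy first chosen in the choice arm. This grouping is already in the Protocol bullet but missing from the SAP.
- For the version that reflects switching, either censor at the switch with time-varying inverse-probability-of-censoring weights or treat strategy as time-varying by scheduled dose. Specify the weight model, and say how participants with no doses are handled.
- State that all doses of facilitated SAT, including observed doses 1, 6 and 12, count as SAT.

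The cost is wording in two documents and a little more analysis. Arm 3 already records time under each strategy and reasons for switching, and dose dates are held in the adherence database. Starting-strategy grouping removes only the dose-count artefact. Confounding from self-selection in the choice arm remains and should be stated with the result.

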# Statistical Analysis Plan: 3HP Options Trial

## OFFICIAL

Full Title	Options for Delivering Isoniazid-Rifapentine (3HP) for TB Prevention (3HP Options Implementation Trial)		
Acronym	3HP Options Trial		
Document History	Version No.	Version Date	Description of Change
	1.0	2021-03-31	Initial release
	1.1	2022-04-26	
 
Change of primary outcome timeline from 16 weeks from date of enrolment to 16 weeks from date of treatment initiation date.
 
Clarification that the per protocol analysis is the equivalent of the secondary outcome of the proportion who complete treatment among those who initiate.
 
Addition of history of prior tuberculosis (TB) as a pre-specified subgroup analysis.
 

Trial Registration	Clinicaltrials.gov: NCT03934931		
Principal Investigators	[name], [name], [name]		

## 1. Introduction

### 1.1 Aim

To compare the uptake of a 3 month (12 dose) regimen of isoniazid and rifapentine (**3HP**) under three delivery strategies: Directly Observed Therapy (**DOT**); Self-administered Therapy (**SAT**); or Patient choice (with the help of a decision aid) of either DOT or SAT among people living with HIV (**PLHIV**) accessing HIV/AIDS care at Mulago Immune Suppression Syndrome (**ISS**; i.e. HIV/AIDS) clinic in Kampala, Uganda.

## 2. Background and Objectives

### 2.1 Specific Objectives

**Primary Objective:** To compare the uptake of 3HP under three delivery strategies: 1) Facilitated DOT; 2) Facilitated SAT; and 3) Informed patient choice (using a decision aid) between facilitated DOT and facilitated SAT. The primary outcome will be defined as the proportion of eligible participants who accept treatment and take at least 11 of 12 doses of rifapentine (**RPT**)/isoniazid (**INH**) within 16 weeks of treatment initiation.

**Secondary Objectives:**

1. To estimate the costs and compare the cost-effectiveness of three strategies for delivering 3HP.
2. To identify processes and contextual factors that influence patient acceptance and completion of 3HP under each delivery strategy.
3. To identify clinic-level barriers to adoption and implementation of 3HP under each delivery strategy.
4. To determine the proportion of patients for whom 3HP treatment is discontinued due to adverse events (**AEs**)/intolerance.
5. To determine the cumulative 16-month incidence of active tuberculosis (**TB**) in each arm.

### 2.2 Primary hypotheses:

1. The proportion who accept and complete 3HP will be highest among PLHIV randomized to the informed choice arm.
2. The proportion of PLHIV who accept and complete 3HP can exceed 80% in a high HIV/TB burden setting.

### 2.3 General comments

This statistical analysis plan covers all effectiveness, implementation, and cost-effectiveness/modelling outcomes. Trial results reporting will follow the CONSORT 2010 statement extension for randomized control trials.

This document summarizes effectiveness outcomes analysis for the primary outcome of the proportion of eligible participants who accept treatment and take at least 11 of 12 doses of RPT/INH within 16 weeks of treatment initiation and secondary outcomes for the implementation and cost-effectiveness of each delivery strategy. These endpoints will be evaluated through review of study documents and study registers for all patients enrolled in the 3HP Options Trial at Mulago ISS Clinic. This Statistical Analysis Plan is written in support of and is predominantly consistent with the full trial protocol version 1.4 (3HP\_Protocol\_Official\_v1.4\_12MAY2022); however, this analysis plan takes precedence.

